We want to investigate this hypothesis in women from 2 or 3 generations in direct link from the same family, such as grandmother, mother and daughter. At birth, mothers transmit gut bacteria to their offspring and therefore the maternal microbiome plays an important role in shaping the early composition of offspring's gut microbiota when compared to fathers. Mother's breast milk also influences the gut microbiome of their offspring in early life. However, there is little information on these maternal influences in the late life of offspring and especially in response to dietary fibre intake. Therefore, we want to determine if there is a transgenerational similarity in gut microbiome composition, metabolic profiles and clinical outcomes in response to 4-week high intake of dietary fibres compared to placebo. This approach (individuals in direct link and female participants across all generations) will allow us to 1) determine if there is a maternal influence on the gut microbiome and responses to dietary fibres of younger generations in late life and 2) have a less heterogenous cohort by focusing on women only which will allow for a better understanding of the data.

2. Study Hypothesis:

We hypothesize that compared to placebo, the dietary fibre intervention will lead to a higher production of short-chain fatty acids by the older generation's gut microbiota when compared to that of the younger generation which will translate into differential responses of gut microbiota composition, glucose, insulin, lipids, gut hormones and inflammatory markers levels.

3. Study Aim:

Investigate the effects of a dietary fibre blend taken over a 4-week period on the production of short-chain fatty acids by the gut microbiota, microbiota composition and health outcomes (glucose, insulin, lipids, gut hormones and inflammatory markers levels) of individuals from 2 or 3 generations in direct link (grandmother, mother and daughter).

4. Primary Outcome:

Comparison of the change in SCFA production from baseline to the end of the intervention between grandmothers, mothers and daughters between dietary fibre intervention and placebo.

5. Secondary Outcomes:

- Comparison of gut microbiota composition from baseline to the end of the intervention between grandmothers, mothers and daughters between dietary fibre intervention and placebo.

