Participants will be asked not to consume any intervention products on the study visit. At the end of study visits 1 and 3, participants will receive 56 sachets of intervention products. At study visits 2 and 4, participants will be asked to bring the empty sachets to assess compliance with the intervention. Throughout the 2 study intervention periods, participants will be asked to complete daily the Intervention Product Reminder sheet whenever they take the intervention product. This will also allow for assessing compliance with the intervention.

Intervention products will be stored in sachets and boxes in the Commonwealth Building of Hammersmith campus, Imperial College London.

8. Participants:

10 duos or trios (20-30 participants) females

Inclusion criteria:

- Any of the following groups of people (in direct descent and from the same family):
 - Grandmother, mother and daughter

- Mother and daughter
- Grandmother and granddaughter
- Age 18-85 (inclusive)
- BMI: 18.5-30 kg/m² (inclusive)
- Considering themselves healthy

Exclusion criteria:

- Intake of antibiotics in the past 3 months and during the study
- Intake of probiotic supplements in the past month and during the study
- Regular intake of laxatives in the past month and during the study
- Subjects with the following conditions:
 - Inflammatory Bowel Disease (IBD)
 - Irritable Bowel Syndrome (IBS)
 - Coeliac Disease
 - Type 12 Diabetes
 - Any type of cancer
 - Autoimmune conditions
 - Conditions that affect the liver
 - Conditions that affect the pancreas
- Subjects who require medical intervention in the coming 3 months
- Smokers
- Shift workers
- Gluten intolerance
- Pregnant and lactating women
- Subjects living in care homes
- had weight changes >5% in the preceding 3 months
- Subjects who are unable to give informed consent by themselves
- Subjects who are currently participating in other clinical trials

Support of number of volunteers:

This is a pilot exploratory study in a new area of research and therefore statistical power calculation is not possible.

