Afterwards, they will have a blood test to check they are not anaemic or diabetic and height and weight measurements will also be taken. They will also have an electrocardiogram (ECG) and blood pressure will be recordedtaken. All women of childbearing age will have a pregnancy test. Participants will also be asked to complete, together with the researcher taking consent, a brief questionnaire assessing their eligibility for the study. Specifically, their weight, height, blood pressure, the result of the pregnancy test will be recorded, as well as any information related to family history of disease, or any medication they are currently taking. In addition, personal information, such as their address (for the collection kits to be sent over), GP details, next of kin will be recorded.

They will also be explained how to use the urine and stool collection kits. Fasted urine and stool samples will be collected by study participants on the day when they come for each study visit. If the results of the blood test will make participants eligible for the study, they will be sent by post the urine and stool collection kits which they will use to bring their samples in on the first study visit. If the blood tests results indicate that they are not eligible for the study, participants will be informed (either by phone or e-mail) by a member of the research team that they will not be able to participate in the study because they do not fit the eligibility criteria.

During the health screening visit, participants will also be explained how to complete the 3 days food diary. If the results of the blood test will make participants eligible for the study, they will be sent by post the first 3 days food diary which they will bring filled in with what they ate and drank 3 days before the first study visit. Eligible participants (once the blood tests results will come and indicate that participants are eligible to participate) will also be sent by post a questionnaire related to demography and dietary habits.

Participants will be advised not to start any strenuous physical activities or go on new diets as these may lead to conflicting results. They will also be asked to consume a similar evening meal the day before each study visit (to ensure consistency between study visits), avoid alcohol the day before each study visit and fast overnight (for 12h) before each study visit (drinking water will be fine).

Visits 1, 2, 3 and 4– Study Visits

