There is a 4-week gap (28 days +/-4 days) between Study Visits 1 and 2, followed by a 4-week wash-out period (28 days +/-7 days) and then followed by Study Visits 3 and 4 (4-week gap 28 days +/-4 days between Study Visits 3 and 4) (Figure 1).

[figure not shown]

Figure 1. Diagram of study visits; V=study visit

Participants will come fasted at the Study Visits and they will not have consumed any intervention products in the morning. They will bring their stool and urine samples, the 3 days food diaries and the participants questionnaire. They will also undergo a physical examination (body weight, height and fat percentage) and have their blood pressure measured and recorded. Women of childbearing age will have a pregnancy test at the beginning of each study visit. If the pregnancy test result is positive, they will be withdrawn from the study. No more data and samples will be collected from them. All the data and samples that were collected up to their withdrawal will be used in data analysis.

At Study Visits 2 and 4 participants will be asked to complete a Visual Analogue Questionnaire where they will rate how the dietary intervention has affected various gastrointestinal symptoms, such as constipation, bloating, appetite.

At 09:30 an intravenous cannula will be inserted into one arm for blood sampling by an adequately trained doctor, nurse or member of research team under aseptic conditions. Just before 10:00 fasting blood samples will be taken through an intravenous peripheral cannula (-15min and -5min). Participants will then receive a standardised breakfast at 10:00.

Postprandial blood samples will be taken at 15, 30, 45, 60, 90, 120 180 and 240 minutes after having the standardised breakfast to measure gut hormones, lipids, glucose, and insulin and inflammatory marker levels. 10ml of blood samples will be

taken at each sampling point, and therefore 100ml (10 x 10ml) during each study visit will be taken (Figure 2).

[figure not shown]

Figure 2. Diagram of Study Visit protocol; VAS=Visual Analogue Scale

Appetite and wellbeing will be assessed at the following timepoints (Figure 2): -15, 0, 30, 60, 120,180 and 240 minutes using a visual analogue scale (VAS).

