After the last sampling point, the canula will be removed and participants will be given an ad libitum standardised lunch which participants will be allowed to eat until they feel comfortably satiated. This will allow us to determine whether the long-term intake of the dietary intervention product had any impact on participants' appetite when compared to baseline. The bowl with pasta will be weighed before and after they had the meal to determine how much food the participants consumed.

At the end of Study Visits 1 and 3, participants will receive 56 sachets with intervention products as outlined in section 7. At study visits 2 and 4 participants will bring the empty intervention sachets and completed Intervention Product Reminded sheet to assess compliance with the intervention.

10. Samples storage and analysis

Samples will be stored in -80°C or -20°C freezers during the clinical trial until ready to be analysed. Samples will be stored in pseudonymised form. Upon enrolment and after signing the informed consent form, each participant will receive an enrolment I.D. that will keep their identity confidential.

Samples analysis will be carried out at Imperial College laboratories. Blood test (that assess participant's eligibility) and urine analysis for pregnancy test will be analysed

immediately. Stool, urine and blood samples collected during the study visits will be stored in freezers until ready to be analysed and then safely disposed. Samples may need to be transported abroad to carry out the same analyses described below. If this happens, samples will be transported securely and safely. Samples will be transported in pseudonymised form. At the end of the clinical trial and after all desired analyses were conducted, the remainder samples will be kept under the authority of Imperial Healthcare Tissue Bank for 10 years for any future ethically approved research studies in accordance with the Human Tissue Act except for samples whose participants did not consent to this on their consent form. In this instance, these will be safely disposed of.

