The collected samples (stool, urine and blood) will be analysed for: gut microbiota composition (from stools) through 16S rRNA sequencing and qPCR (quantitative Polymerase Chain Reaction); metabolites produced by the gut microbiota (from stools and urine) thorough NMR (Nuclear Magnetic Resonance), GC-MS (gas chromatography coupled with mass spectrometry), LC-MS (liquid chromatography coupled with mass spectrometry), LC-MS (liquid chromatography coupled with mass spectrometry), blood glucose, insulin, gut hormones (PYY and GLP-1), inflammatory markers (C reactive protein) and lipid levels.

11. Statistical Analysis

Statistical tests, such as ANOVA (Analysis of Variance) and t-tests (paired and unpaired) will be used to compare different groups: study participants groups, dietary fibre groups and placebo groups. Correlation analysis (Pearson and/or Spearman) and linear models will be used to analyse the relationship between gut bacteria taxa, short-chain fatty acids levels, metabolites levels, food diary information and demographics. Statistical significance levels will be p<0.05.

Various platforms will be used to analyse the data. Gut microbiome composition will be analysed using 16S rRNA sequencing on Illumina MiSeq and statistical analyses will be performed in R. Species diversity and richness will be calculated and statistical tests include t-tests and Mann-Whitney U tests, statistical significance p<0.05. Species diversity and richness and their changes from baseline between grandmother, mother and offspring will be compared. Data from placebo and dietary fibre intervention will be compared.

Short-chain fatty acids (SCFA) production from stool samples will be measured using GC-MS (Gas Chromatography coupled with Mass Spectrometry). T-tests (paired and/or unpaired) and ANOVA tests will be used to determine whether there are significant differences in SCFA production between grandmothers, mothers and offspring from baseline to end of intervention. Data from placebo and dietary fibre intervention will be compared. Significance levels will be p<0.05.

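### Sachets and schedule cover 28 days but the end visit may fall up to 32 days after dispensing, so an adherent woman can give her primary SCFA sample 1 to 3 days off product

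*Combined protocol and SAP*

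**What the plan says.** **Dose and supply (section 7).** Participants take two doses a day for 28 days: 10 g/day on days 1 to 4, 20 g/day on days 5 to 12 and 30 g/day on days 13 to 28. Nothing is specified after day 28. On supply: "At the end of study visits 1 and 3, participants will receive 56 sachets of intervention products". Section 9 repeats this: "At the end of Study Visits 1 and 3, participants will receive 56 sachets with intervention products as outlined in section 7". The handover comes after the last blood sample, when "the canula will be removed and participants will be given an ad libitum standardised lunch".

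**Visit timing (section 9, Visits 1 to 4).** "There is a 4-week gap (28 days +/-4 days) between Study Visits 1 and 2", and the same tolerance applies between Visits 3 and 4.

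**Visit day.** Section 7 asks participants to take no product on a study visit. Section 9 says of arrival at the visits that "they will not have consumed any intervention products in the morning".

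**Primary outcome and specimen.** Section 4 gives: "Comparison of the change in SCFA production from baseline to the end of the intervention between grandmothers, mothers and daughters", compared across fibre and placebo. Section 9 (Visit 0) says "Fasted urine and stool samples will be collected by study participants on the day when they come for each study visit", and section 11 says "Short-chain fatty acids (SCFA) production from stool samples will be measured using GC-MS".

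**Not stated.** The protocol does not say which calendar day is day 1, what a woman should do if her end visit falls later than her last sachet, or that dosing continues to the evening before the visit.

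**The concern.** The supply has no spare sachets, while the visit window runs four days past the nominal gap. A woman can therefore follow the schedule exactly, attend within the window, and still be off product when she collects the stool for the primary outcome. No protocol deviation is needed.

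This matters because section 1 itself links SCFA production to how much fibre is eaten. The fibre-period sample is meant to show the state at the end of the intervention. If some of these samples follow one or more days without the product, the measured fibre response may be smaller than the response on treatment, and the fibre-placebo difference may be diluted. With only 20 to 30 women, each affected sample carries weight.

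**Working it through.** **Inputs.** Two doses a day; steps of 4, 8 and 16 days at 10, 20 and 30 g/day; 56 sachets per period; no product on visit days (all section 7). End visit 28 ± 4 days after dispensing, so 24 to 32 days (section 9). Stool collected on the visit day (section 9).

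**Assumptions.** One sachet per dose, and first dose on the day after dispensing. The first is supported by the supply check below. The second fits handover at the end of the visit together with the request to take no product that day, but the protocol does not state it.

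**Supply check.** 2 × (4 + 8 + 16) = 56. The plan's figure is reproduced: exactly 28 days, no spares.

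**Formulas.** Let g be the days from Visit 1 to 2 (or 3 to 4).
- Dosing days = min(g − 1, 28)
- Days at 30 g = dosing days − 12
- Product = 4 × 10 + 8 × 20 + 30 × (dosing days − 12) g
- Sachets left = 56 − 2 × dosing days
- Full product-free days before the visit day = max(0, g − 29)

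| g | Dosing days | Days at 30 g | Product (g) | Sachets left | Product-free days |
|---|---|---|---|---|---|
| 24 | 23 | 11 | 530 | 10 | 0 |
| 25 | 24 | 12 | 560 | 8 | 0 |
| 26 | 25 | 13 | 590 | 6 | 0 |
| 27 | 26 | 14 | 620 | 4 | 0 |
| 28 | 27 | 15 | 650 | 2 | 0 |
| 29 | 28 | 16 | 680 | 0 | 0 |
| 30 | 28 | 16 | 680 | 0 | 1 |
| 31 | 28 | 16 | 680 | 0 | 2 |
| 32 | 28 | 16 | 680 | 0 | 3 |

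With this start, only g = 29 gives both the full 28-day course and a sample on the day after the last dose. At the nominal 28 days, 27 dosing days fit. At 24 days the woman receives 530/680 = 78% of the planned product.

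**Sachets needed to reach the eve of the latest visit.** 2 × (32 − 1) = 62, against 56 supplied: 6 short.

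**How many samples.** There are 2 × 20 to 2 × 30 = 40 to 60 end visits, fibre and placebo periods together. The documents do not say how often gaps of 30 to 32 days occur. Assumed shares of 0%, 10% and 3/9 (an even spread over the nine permitted days) give 0, 4 to 6, and 13 to 20 affected samples. These are illustrations, not estimates.

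**The case against.** **The intent is legible.** A reader might infer that nothing at all ties the last dose to the visit. That goes too far. Telling women to take no product on the day of Visit 2 or 4 presupposes that they are still dosing up to it. What is missing is a working rule for late visits.

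**Several conditions must coincide.** The gap must be 30 to 32 days, and the woman must start the next day. If she happened to start 1, 2 or 3 days later than that, at gaps of 30, 31 or 32 respectively, the problem would disappear. She must also either stop at day 28 as written or have almost no sachets left. If she used leftovers after day 28, which the plan does not provide for, they would last to the eve of the visit unless she had taken more than 56/58 = 97%, 56/60 = 93% or 56/62 = 90% of the doses due at gaps of 30, 31 or 32 days. Six of the nine permitted gaps, including the nominal one, have no product-free day. All of this stands. It limits how often the problem arises but does not supply the missing rule.

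**The effect is unknown.** Section 1 relates SCFA production to the amount of fibre eaten, but says nothing about how fast it falls after stopping. A reader might infer that samples at 30 to 32 days are invalid, or that the primary comparison is biased. The documents support neither. The same window applies to both products and both periods, and nothing shows that late visits are more common in one arm or generation.

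**The last dose date is partly recoverable.** The daily reminder sheet and returned empty sachets would let staff reconstruct it, although section 7 describes them only as compliance checks. That helps afterwards; it does not prevent the gap.

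**This is an exploratory pilot** with no power calculation, so the point calls for a short clarification. That is accepted.

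**Conclusion.** The point holds as a minor one. Followed exactly, the stated supply and schedule give an off-product primary sample at three of the nine permitted gaps: 1, 2 or 3 full product-free days at 30, 31 or 32 days, and none at 24 to 29. This rests on one sachet per dose, a first dose on the day after dispensing, full adherence and no dosing after day 28.

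A reader might also infer that 29 days is the only workable gap whatever the start day. That is not so: a start counted back from the visit would give a full course and no product-free day at 29 to 32 days. The statement is true only for a next-day start. Nor should the gap be lengthened by supposing a first dose at dinner on the dispensing day, because that sits badly with the instruction to take no product on a study visit.

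The direction of any effect, dilution of the fibre-placebo difference, is plausible from the protocol's own reasoning. Its size and frequency cannot be derived from the documents.

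**What to change.** In section 7:

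1. Define day 1 as the day after Visit 1 or 3.
2. Dispense 62 sachets per period (6 extra of 15 g).
3. Instruct participants to continue 30 g/day until the evening before Visit 2 or 4.
4. Where possible, book Visits 2 and 4 no earlier than day 29.

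Steps 1 to 3 remove the product-free days at every permitted gap. Step 4 is needed because extra sachets do not repair early visits. With it, every adherent woman completes at least 28 dosing days. At g = 29 she has 16 days at 30 g and 680 g; at g = 32 she has 31 − 12 = 19 days at 30 g and 200 + 570 = 770 g.

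**Cost.** Extra sachets are 6 × 2 × 20 = 240 to 6 × 2 × 30 = 360 in total. Dosing can run up to 3 days beyond the stated 28. With the day-29 minimum, the booking window shrinks from nine days to four, which is harder for families of two or three women. Without it, exposure spans 11 to 19 days at 30 g and 530 to 770 g, against 11 to 16 days and 530 to 680 g as now written. Compliance would have to be counted against the 2 × (g − 1) doses due, not against the number dispensed.

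**Second choice.** Book the visit at 29 to 32 days and set the first dose g − 28 days after Visit 1 or 3, so that day 28 is the eve of the visit. This gives 28 dosing days and 680 g from the present 56 sachets. It is less robust because the product always runs out the evening before the booked visit, so each day of postponement adds a product-free day.

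### The inclusion rule admits grandmother-granddaughter pairs linked through a son, which cannot inform the maternal-influence question, and nothing planned identifies them

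*Combined protocol and SAP*

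**What the plan says.** Section 8 sets the sample at 10 families of two or three women, 20 to 30 participants in all. A family qualifies as a three-generation trio, as a mother-daughter duo, or as "Grandmother and granddaughter". The condition common to all three is that the women be "in direct descent and from the same family". Neither the inclusion nor the exclusion list mentions the sex of the parent who links a grandmother to her granddaughter.

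Section 1 explains why related women are recruited. It states that "At birth, mothers transmit gut bacteria to their offspring and therefore the maternal microbiome plays an important role in shaping the early composition" of the child's microbiota, draws the contrast with fathers, and adds breast milk as a second route. It then gives two purposes for the direct-link, all-female approach. The first is to "determine if there is a maternal influence on the gut microbiome and responses to dietary fibres of younger generations in late life". The second is to "have a less heterogenous cohort by focusing on women only". Section 1 also states an interest in similarity across generations in the microbiome, metabolic profiles and clinical outcomes.

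**The concern.** The eligibility rule is wider than the rationale. Transmission at birth and through breast milk runs from a mother to her own child. In a pair linked through a son, the grandmother's transmission went to the son. The granddaughter's exposure at birth and through her mother's milk came from a woman outside the grandmother's line. Any resemblance between the two may be real, but it cannot be attributed to the route that Section 1 sets out to examine.

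With 10 families, each is one tenth of the family-level information if families count equally. If such pairs enrol unidentified, an analysis of maternal influence or family similarity would mix two kinds of pair. A weak result could then reflect the mixture, and a positive one could not be read cleanly as maternal.

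**Working it through.** The plan gives no figure on this point, so there is none to reproduce. The check has three parts.

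**1. Does direct descent force a female line in each group?** (Inputs: the three groups and the common condition in Section 8.)

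- Mother and daughter: the link is maternal by definition.
- Trio: the mother must descend from the grandmother and the daughter from the mother. A paternal grandmother with her daughter-in-law and granddaughter would fail, because the daughter-in-law does not descend from her. The line is maternal.
- Grandmother-granddaughter duo: a son's daughter descends directly from his mother. The pair meets the written condition, and the line is not maternal.

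The gap is confined to the third group.

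**2. Does another section close it?**

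- Section 1 describes the population as "women from 2 or 3 generations in direct link from the same family, such as grandmother, mother and daughter". The words introducing the chain make it an example, not a condition.
- Section 3 (Study Aim) and the Visit 0 text in Section 9 put the three-generation chain in parentheses. This suggests a female line, but neither is an eligibility rule, and Section 8 explicitly allows a duo without the mother.
- The items listed for the Visit 0 questionnaire include illness in the family and next of kin, but not line of descent. A posted questionnaire on demography and diet is mentioned without its contents.
- Section 11 (Statistical Analysis) does not separate maternal-line from paternal-line pairs.

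No section closes the gap. Section 8 sets no limit on the number of such duos, so 0 to 10 of the 10 families could be paternal-line. That range is only what the rule permits; the documents forecast no split.

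**3. How much could a family-similarity measure be diluted?** The documents give no resemblance figures, so these are assumptions: maternal-line resemblance 0.3, paternal-line resemblance *r* between 0 and 0.3, families weighted equally. With *k* paternal-line families out of 10:

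average = [0.3 × (10 − *k*) + *r* × *k*] / 10

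| *k* | *r* = 0 | *r* = 0.2 | *r* = 0.3 |
|---|---|---|---|
| 2 | (2.4 + 0)/10 = 0.24 | (2.4 + 0.4)/10 = 0.28 | (2.4 + 0.6)/10 = 0.30 |
| 4 | (1.8 + 0)/10 = 0.18 | (1.8 + 0.8)/10 = 0.26 | (1.8 + 1.2)/10 = 0.30 |

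Equal weighting matters. A trio contains three pairs and a duo one, and a paternal-line family is always a duo. If pairs were weighted equally and all other families were trios, then at *r* = 0 two paternal-line duos would give 0.3 × 24/26 = 0.28, and four would give 0.3 × 18/22 = 0.25.

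**The case against.** The strongest reply is that the trial is not mainly about maternal transmission. The hypothesis, aim and primary outcome concern responses to fibre and placebo across generations. The secondary outcomes are generation comparisons or correlations with food diaries. A paternal-line pair supplies one older and one younger woman, each with both treatment periods, and the sex of the linking parent does not affect those comparisons. This stands. A reader might infer that the primary outcome is compromised, or that the design exists only to study maternal transmission; the documents support neither.

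Second, Section 11 defines no within-family correlation, so the dilution figures describe a statistic that the plan does not specify. This also stands. The figures are illustrative, and zero paternal-line resemblance is an extreme, because such pairs may share genes or diet. What survives is that Section 1 states the question, and the enrolled pairs limit what can be said about it.

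Third, paternal-line pairs might be useful as a contrast, since a cohort made up only of female lines cannot separate maternal transmission from general family resemblance. That is fair, but the contrast is available only if the pairs are identified.

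Fourth, one might say that the analyst could never remove these pairs. That goes too far. Line of descent is a fixed fact that can be asked at any contact, and the unseen questionnaire might capture it. The documents show only that it is not a listed item and that no analysis uses it.

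Finally, the investigators may have intended a female line. The parenthetical wording hints at it, but the eligibility rule does not say so.

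**Conclusion.** The point holds, within limits. As written, Section 8 admits paternal-line grandmother-granddaughter pairs, and the plan neither identifies nor separates them. The consequence falls on the maternal-influence and transgenerational-similarity question in Section 1, not on the generation-by-treatment comparisons.

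The size is unknown. It depends on how many such pairs enrol, which the documents do not indicate, and on resemblance values that they do not supply. Under the stated assumptions the effect runs from none, when paternal-line resemblance equals maternal-line resemblance, to a fall from 0.30 to 0.18 with 4 such families. Even where there is no dilution, resemblance in those pairs could not be credited to birth or breastfeeding. The conclusion that the rule admits these pairs rests on the text alone and needs none of the assumptions.

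**What to change.** 1. Add line of descent (maternal or paternal) to the eligibility questionnaire already completed at Visit 0. Ask it retrospectively of families already enrolled.
2. State in Section 11 that paternal-line pairs are left out of, or analysed separately in, any maternal-influence or family-similarity analysis, and are kept in the generation comparisons, including the primary outcome.
3. Preferably, for new families, reword the third group in Section 8 to *Maternal grandmother and granddaughter*.

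The first two steps cost one question and one sentence and exclude nobody. The third has a real recruitment cost. Each granddaughter has one maternal and one paternal grandmother, so if both are equally available the restriction could remove up to about half of the potential duos of this type. The other two groups are unaffected. If recruitment cannot bear that, the first two steps still keep the maternal-influence analysis interpretable.
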